7.8.3 Major Complications

Major Complications are adverse events which may occur in conjunction with or following atrial ablation that are included in the primary safety endpoint for this study. The list and definitions for adverse events that are considered Major Complications are outlined in **Appendix L**.

Should a Major Complication occur, the investigator is required to report by eCRF all available information regarding the Major Complication to the Sponsor promptly upon learning of the event. Additional time may be required in order to obtain the background details related to a Major Complication; however, the report of its occurrence should be made to the Sponsor once the investigator first learns of the event. All related medical records will be required for submission to Hansen Medical for Major Complications that are reported.

All potential Major Complications reported will be reviewed and adjudicated by the CEC. Major Complications will be classified as either a Primary Safety Endpoint or a Chronic Safety Event depending on the event occurrence following the ablation procedure, (Refer to definitions in Sections 5.2 and 5.4).

7.8.4 Unanticipated Adverse Device Effects

An unanticipated adverse device effect (UADE) is defined as "any serious adverse effect on health or safety or any life-threatening problem or death caused by, or associated with, a device, if that effect, problem or death was not previously identified in nature, severity, or degree of incidence in the investigational plan or application (including a supplementary plan or application), or any other unanticipated serious problem associated with a device that relates to the rights, safety, or welfare of subjects" (21 CFR Part 812.39).

The investigator must notify the Sponsor and IRB/EC of any UADE occurring during the clinical study no later than 10 working days after the investigator learns of the event. All UADEs must be documented by the investigator including the date of onset, a complete description of the event, possible reason(s) for the event, severity, duration, actions taken and outcome. Copies of all supporting documents should be sent to Hansen Medical.

Any UADEs that occur during the course of the Study will be reported to the participating investigators and their IRBs/ECs. A report from the Sponsor will be submitted to the FDA no later than 10 working days after being notified by the investigator.

7.9 Mechanical Failures or Malfunction

If study device failures or malfunctions occur, contact Hansen Customer Service at [name], and refer to the Return Material Authorization (RMA) process in **Appendix J**.

Examples of possible device malfunctions include:

- Packaging is defective,
- Device physically deforms or breaks, even if caused by user error,
- Device fails to perform as intended.

7.10 Medical Device Vigilance reporting (EU sites)

For European investigational sites, the Medical Device Vigilance System will be used to report incidents to the appropriate regulatory agencies.

7.11 Data and Safety Monitoring Board

The Data and Safety Monitoring Board (DSMB) is comprised of an independent group of experts serving in an individual capacity to provide their expertise and recommendations to Hansen Medical concerning the conduct of the study. The board is composed of members including a biostatistician and physicians from one or more of the following disciplines: cardiology, neurology, and/or cardiac electrophysiology. This board will assemble to review the results of each interim analysis or on an urgent basis (as needed) to review all CEC-adjudicated Major Complications and device-related adverse events. The board has the responsibility to advise the Sponsor about the appropriateness of continuing, or terminating the study based on the findings of their review. The board will generate reports to support their findings.

7.12 Data Collection and Evaluation

Data gathered during the course of the study will be documented through electronic data capture (EDC). Missing, incomplete or inconsistent data will be requested from the investigation site personnel and appropriate corrections will be made. An audit trail will identify all changes and corrections to the electronic data. Training on the use of the EDC system along with instructions for completion of the EDC eCRFs will be provided to the study site personnel by Hansen Medical or its designee.

7.13 Source Documentation

Regulations require that an investigator maintain information in the study subject's medical record to corroborate data collected on the eCRF. To comply with these regulatory requirements, all medical records pertaining to each subject's participation in the study should be maintained and made available as required by Hansen Medical and/or its designee as well as regulatory inspectors. Access to original medical records must be provided. Complete medical (clinical and hospital) records include but are not limited to the following documentation.

- Medical history/physical condition of the subject before involvement in the study, date and reports on study required testing sufficient to verify clinical protocol entry criteria.
- Description of device usage during study procedure (procedural logs, drugs administered during the procedure, device identification information and disposition, date, time, imaging results and clinical findings, study specific worksheets etc.).
- Signed notes in the subject's medical record on the enrollment day that identify and include: the subject's date of enrollment, procedure date, the study sponsor (Hansen Medical), site name, the subject's assigned study identification number, and documentation and confirmation that the appropriate informed consent was obtained from the subject.
- Dated and signed notes for each subject's study-required visit.
- Lab test results.
- All ECG, Ultrasound, CT, MR and any other imaging reports, etc.
- Dated printouts or reports of special assessments (ECG report, imaging report, laboratory results etc.).
- Adverse event reporting and follow-up of the adverse event. Information in the medical record should include at a minimum the following: event description, severity, seriousness, onset date, date site became aware of event, duration, relation to study device, treatment, and outcome of the adverse event.
- Study subject's condition upon completion of or withdrawal from the study. This includes number and type of attempts to ensure subject compliance to study-required visits.

Source Documentation must be available at all times for inspection by the study monitors and regulatory inspectors.

7.14 Protocol Deviations/Violations

A protocol deviation occurs when a clinical investigator and/or study site personnel do not conduct the study according to the clinical investigational plan (protocol). All deviations must be recorded on the eCRF: Protocol Deviation. United States regulations (21 CFR 812.140) require that investigators maintain accurate, complete, and current records relating to the clinical study. This includes documents showing the dates and reasons for each deviation from the clinical investigational plan. Depending upon the nature of the protocol deviation, expedited reporting and prior approval from Hansen Medical may be

required. All deviations will be summarized and submitted in IDE progress reports, annual reports, and the final study report to the FDA.

If Hansen Medical finds that an investigator is not complying with the executed study agreements, the investigational plan, the FDA regulations, or the requirements of the reviewing IRB, prompt action will be taken to secure compliance. In addition, the participation of the investigator may be terminated (21 CFR 812.46). Additional information is provided in Section 13.4 – Study Termination.

7.14.1 Deviations with Expedited Reporting Requirements

For the following types of protocol deviations (per 21 CFR 812.150), an investigator is required to notify Hansen Medical and the IRB within 5 business days of the deviation.

- Emergency Deviation from the Investigational Plan (a deviation to protect the life or physical well-being of a subject in an emergency).
- Failure to Obtain Informed Consent from the subject.
- Failure to apply any of the inclusion and exclusion criteria for subject enrollment into the study.

Notification to Hansen Medical and/or the IRB should be documented and maintained in the clinical study file at the site and at Hansen Medical.

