Prior to the start of any ablation procedure, the subject's echocardiogram will be reviewed to ensure no evidence of left atrial thrombus. A routine EP study may be performed to evaluate the location, morphology, and dimensions of each pulmonary vein by venogram. Intra-cardiac echocardiography (ICE) may also be performed prior to the ablation procedure at the physician's discretion.

A subject is required to meet all the inclusion and none of the exclusion criteria to participate in the study. Enrollment occurs when a subject signs the Informed Consent Form. The subject must then meet all additional intra-procedural enrollment criteria (i.e. no intramural thrombus, etc.). If the subject does not meet all intra-procedural enrollment criteria, the subject will not be treated with the study device and will be withdrawn from the study. The screening, baseline, and withdrawal case report forms should be completed. The investigator shall report any acute procedural adverse events on the adverse event form.

These subjects who are withdrawn prior to the procedure will count against the maximum enrollment limit. However, the company requests that the maximum enrollment limit is increased accordingly to account for those who signed the Informed Consent Form but did not undergo the study procedure.

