6.7 Data Analysis

All statistical analyses will be done using the SAS software version 9.3 or later (Copyright © 2000 SAS Institute Inc., [name], USA. All rights reserved), R software or StatXact (Copyright © 2010, 1989-2012, Cytel Software Corporation).

All data will be collected as detailed in the clinical trial schedule. Subject demographics, medical history, risk factors, procedure characteristics, and outcome variables will be summarized using descriptive statistics for continuous variables (e.g. mean, standard deviation) and frequency tables or proportions for discrete variables.

The “Intention to Treat” (ITT) population includes all enrolled subjects. This includes subjects who signed an informed consent form. Subjects who are not enrolled due to not meeting the intra-procedural criteria are considered to be withdrawn from the study. Subjects who have already had a 14F introducer sheath introduced who subsequently are withdrawn during the procedure prior to treatment with the study device will be monitored for any acute adverse events related to the introduction of the 14F introducer sheath. Acute safety data for these subjects will be reported as a separate cohort, since these subjects are not treated with the study device. Additional subjects may be enrolled to replace subjects who were withdrawn due to not meeting the intra-procedural enrollment criteria. The primary statistical analysis will be performed on the cohort of subjects who are enrolled, meet the intra-procedural enrollment criteria, and are treated with the study device.

The following additional endpoints will be analyzed but will not be tested for statistical significance and will be reported as proportions, or means and standard deviations.

- Length of hospital stay,
- Total ablation time,
- Total ablation energy,
- Total fluoroscopy time,
- Total procedure time,
- Non-AF targets ablated manually,
- Ablative lesion sets in addition to those required for pulmonary vein isolation,

- Adverse events,
- Serious Adverse Events,
- Chronic success rates for subjects with a single procedure.

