7.0 Study Procedures

7.1 Inclusion and Exclusion Criteria

Subject Inclusion and Exclusion Criteria - Subjects are required to meet all the inclusion/exclusion criteria to be eligible for participation (including intra-procedural criteria).

The following sections outline the specific inclusion and exclusion criteria for the study. Subjects who meet **all** of the general inclusion criteria and **none** of the exclusion criteria will be eligible for study participation.

Inclusion Criteria

To be eligible for enrollment in the study the following criteria must be met:

1. Subjects with paroxysmal atrial fibrillation who have had two or more spontaneously terminating episodes of atrial fibrillation that last longer than 30 seconds and shorter than 7 days, in the nine months prior to enrollment. At least one episode must be documented with ECG, transtelephonic monitoring (TTM), Holter monitor, or telemetry.
2. Failure of at least one Class I – IV anti-arrhythmic drug (AAD) for PAF as evidenced by recurrent symptomatic PAF, or intolerable side effects due to AAD. AADs are defined in **Appendix B**.
3. Signed informed consent.
4. Age 18 years or older.
5. Able and willing to comply with all pre-, post-, and follow-up testing and requirements.

Exclusion Criteria:

Subjects are **ineligible** for enrollment in the study if they meet **any** of the following criteria:

1. Atrial fibrillation secondary to electrolyte imbalance, thyroid disease, or reversible or non-cardiac cause.
2. Previous ablation for atrial fibrillation.
3. Atrial fibrillation episodes that last less than 7 days and are terminated by cardioversion.
4. Previous valvular cardiac surgery procedure.
5. Cardiac artery bypass graft procedure within the previous 180 days.
6. Previous septal defect repair.
7. Expecting cardiac transplantation or other cardiac surgery within the next 180 days.
8. Coronary PTCA/stenting within the previous 180 days.
9. Documented left atrial thrombus on ultrasound imaging (TEE).
10. Documented history of a thrombo-embolic event within the previous 365 days.
11. Diagnosed atrial myxoma.
12. Presence of an implanted ICD.
13. Presence of permanent pacing leads.
14. Significant restrictive, constrictive, or chronic obstructive pulmonary disease or any other disease or malfunction of the lungs or respiratory system with chronic symptoms.
15. Significant congenital anomaly or medical problem that in the opinion of the investigator would preclude enrollment in this study.

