- If subject meets any of the intra-operative exclusion criteria, withdraw the subject from the study. The screening, baseline, and withdrawal case report forms should be completed. Any acute procedural adverse events shall be reported on the adverse event form.

- The ablation catheter shall be inserted into the Artisan catheter. If the ablation catheter does not fit smoothly through the Artisan catheter, the poorly fitting catheter should not be used and should be replaced with another catheter.
- Ablation of the cavotricuspid isthmus may be performed only in subjects with a history of typical atrial flutter or inducible cavotricuspid isthmus dependent atrial flutter.
- SVC isolation shall be performed if AF triggering potentials are noted in the SVC.
- The ablation catheter will be remotely manipulated to map and ablate within the atria.
 - The ablation catheter shall be placed within the Artisan catheter and manually introduced into the subject under fluoroscopic guidance.
 - A CARTO or EnSite Velocity three-dimensional electroanatomic mapping system shall be used to map the anatomical locations of pulmonary veins and ablative lesions.
 - A circumferential anatomical approach shall be used to electrically isolate the pulmonary veins.

Recommended Ablation Parameters:

Place ablative lesions 1-2 cm outside of the pulmonary veins in order to minimize the risk of pulmonary vein stenosis. Target Sensei® IntelliSense readings of 10-20g, with a maximum of 40g, during lesion creation.

RF power should typically be set to 20-25W with a nominal maximum power of 30W. Starting at 20-25W in an anatomical region, RF power may be increased after 15 seconds in 5W increments to achieve a transmural lesion as shown by local atrial electrogram attenuation or splitting. Ablation duration at a single anatomical lesion location is recommended to be limited to 30 seconds. If the ablation output time for the RF generator is set for longer than 30 seconds, the ablation catheter should be moved so that the ablation duration in a particular location doesn't exceed 30 seconds.

When ablating on the posterior left atrial wall, power should be reduced to mitigate the occurrence of an atrio-esophageal fistula. RF power should typically be set to 15-20W, and should not exceed 20W. Esophageal temperature should be monitored and energy delivery should be terminated if the esophageal temperature reaches or exceeds 41°C, as measured from the esophageal temperature probe.

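### The primary cohort requires subjects both to meet the intra-procedural criteria and to be treated, so a subject treated in breach of those criteria drops out of the 16% safety test

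*Protocol*

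**What the plan says.** Protocol section 6.7 names three groups.

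- **ITT:** "The “Intention to Treat” (ITT) population includes all enrolled subjects". Enrolment means signing consent (sections 5.0 and 15.0). No primary test is stated for this set.
- **Primary analysis:** "subjects who are enrolled, meet the intra-procedural enrollment criteria, and are treated with the study device".
- **Separate acute-safety cohort:** subjects who had the introducer sheath placed but were withdrawn before treatment. "Acute safety data for these subjects will be reported as a separate cohort, since these subjects are not treated with the study device".

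Section 5.0 sets the rule for sites: "If the subject does not meet all intra-procedural enrollment criteria, the subject will not be treated with the study device and will be withdrawn". Section 7.3.3 repeats it: "If subject meets any of the intra-operative exclusion criteria, withdraw the subject from the study". Section 5.0 describes the intra-procedural criteria by one example, intramural thrombus, and leaves the rest of the list open.

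Two other places bear on breaches. Section 7.1 counts the intra-procedural criteria among the eligibility criteria. Section 7.14.1 requires notice to the sponsor and the IRB within 5 business days for "Failure to apply any of the inclusion and exclusion criteria for subject enrollment into the study". It attaches no analysis rule.

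Section 6.1 declares safety success when at least 95% of the posterior for the Major Complication rate lies below 16%.

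**The concern.** A complication rate tested against a fixed goal should count everyone exposed to the device. Section 6.7 makes membership depend on treatment and also on having met the intra-procedural criteria. Someone who was treated but had failed one of those criteria satisfies the first condition and not the second.

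Three features make this more than a drafting nicety.

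- The criteria are an open list and the trial is single-arm, so whether a treated subject met them could be judged after the outcome is known.
- The one example given, intramural thrombus, plausibly bears on stroke and thromboembolism, which section 5.2 counts as Major Complications. Exclusion could therefore be related to the endpoint.
- The rule is uneven. A treated subject who breached a pre-procedure criterion remains enrolled and treated, and so stays in the test.

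**Working it through.** **Step 1. Where each subject falls under section 6.7 as worded**

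| Subject | Primary cohort | Separate cohort | ITT |
|---|---|---|---|
| Fails an intra-procedural criterion, not treated | No | Yes, if the sheath was introduced | Yes |
| Treated, breached a pre-procedure criterion only | Yes | No | Yes |
| Treated, failed an intra-procedural criterion | No | No (covers untreated subjects only) | Yes, but no test stated |

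The third row is the gap.

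**Step 2. Inputs**

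- From the protocol: goal 16% and posterior threshold 0.95 (6.1); effectiveness goal 54% with the same threshold (6.2); 125 to 250 subjects, 5% withdrawn before the procedure, and 98% probability of success at true rates of 8% and 72% (6.5).
- Assumed: a Beta(1,1) prior, because the prior is left to Appendix M, which is not shown; a single look; and, in step 5, a breach rate and a complication risk for violators, neither of which the documents give.

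**Step 3. Cut-offs and the plan's own figure**

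With y events in n subjects the posterior is Beta(1 + y, 1 + n − y). Safety passes if P(rate < 0.16) ≥ 0.95. The largest passing y is 13 at n = 125 (0.953) and 30 at n = 250 (0.956). Effectiveness needs at least 77 and 148 successes.

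Exact binomial power at 8% and 72%, treating the two endpoints as independent:

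- n = 250: 0.990 × 1.000 = 0.990
- n = 238 (250 less 5%; at most 28 events, at least 142 successes): 0.984 × 1.000 = 0.984
- n = 125: 0.874 × 0.996 = 0.870

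A simplified simulation allowing success at any look from 125 to 250 gives 0.993. The stated 98% is reproduced to within 2 points, so the cut-offs are a fair approximation. The 98% itself does not depend on this point.

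**Step 4. Excluding treated violators who had an event**

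| All treated | Posterior | Excluded | Analysed | Posterior | Result changes? |
|---|---|---|---|---|---|
| 31/250 | 0.936 | 1 | 30/249 | 0.953 | Yes |
| 32/250 | 0.909 | 2 | 30/248 | 0.951 | Yes |
| 14/125 | 0.920 | 1 | 13/124 | 0.949 | No |
| 14/125 | 0.920 | 2 | 12/123 | 0.970 | Yes |
| 15/125 | 0.873 | 3 | 12/122 | 0.967 | Yes |

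The third row misses narrowly and depends on the prior. With Beta(0.5, 0.5) the same case goes from 0.934 to 0.959 and would change.

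**Step 5. Chance of passing safety when the true rate among all treated is 16%**

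Let f be the fraction treated in breach and r their complication risk. The rate in the remainder is p = (0.16 − f × r)/(1 − f). For example, f = 0.02 and r = 0.50 give (0.16 − 0.01)/0.98 = 0.153. The number excluded, v, is Binomial(N, f), and the pass probability is the sum over v of P(v) × P(Binomial(N − v, p) ≤ cut-off at N − v). Excluded subjects are not replaced.

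| N | All treated | f = 1–2%, r from 16% to 50% | f = 5%: r = 16% / 32% / 50% |
|---|---|---|---|
| 125 | 0.051 | 0.036 to 0.055 | 0.042 / 0.068 / 0.113 |
| 250 | 0.047 | 0.043 to 0.077 | 0.044 / 0.087 / 0.168 |

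With rare breaches or ordinary risk the effect is small, and at N = 125 the pass probability can even fall. It becomes material only if breaches reach several percent and carry high risk.

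**The case against.** The best defence is that section 6.7 describes a sequence: consent, pass the check, be treated. Sections 5.0 and 7.3.3 bar treatment of anyone who fails the check, and in 7.3.3 the instruction to withdraw comes before the ablation catheter is inserted. The reason 6.7 gives for the separate cohort is that those subjects were not treated, which suggests treatment is the intended dividing line. On that reading a thrombus missed at the check belongs to a subject who passed it. Nor would a complication be hidden: adverse events are collected from consent, potential Major Complications go to the events committee, deviations are reported to FDA, and monitoring is 100%.

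Much of this stands. Breaches should be rare, and a reader might infer more than the text supports in three ways.

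- **That the plan expects violators to be treated.** Section 7.14.1 is a reporting rule. It shows only that a failure to apply criteria is recognised as possible.
- **That any eligibility breach removes a subject.** Section 6.7 names only the intra-procedural criteria.
- **That treated violators may be withdrawn and replaced.** Sections 5.0, 6.5, 6.7 and 7.3.3 provide for withdrawal and replacement only before treatment, and no passage sets up a retrospective eligibility decision.

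What the defence does not supply is a sentence keeping a treated intra-procedural violator in the primary cohort. An instruction to sites does not say how a breach is analysed, and reporting an event is not the same as counting it in the test. Assignment of violators is often left to a statistical analysis plan, but here the protocol itself fixes the cohort.

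**Conclusion.** The point holds in a narrow form and is minor. As worded, section 6.7 leaves a subject treated in breach of an intra-procedural criterion out of the 16% safety test, and no other stated cohort tests that subject's events. The open list of criteria allows the question of membership to be settled after the outcome is known.

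The consequence is confined to borderline results. One excluded event can change the safety conclusion at 250 subjects and two can at 125. One at 125 changes nothing under the Beta(1,1) prior, though only by a small margin. These figures rest on the assumed prior and a single look. No expected inflation of false success can be stated, because the documents give neither a breach rate nor a risk for such subjects, and step 5 shows how far the answer moves with those assumptions. A false safety pass is also not a false study success, since effectiveness must be met as well.

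**What to change.** In section 6.7, define the primary cohort for both endpoints as all enrolled subjects treated with the study device, regardless of any eligibility deviation identified, before or during the procedure. Show the cohort without intra-procedural violators only as a sensitivity analysis. That set needs a definite boundary, so the intra-procedural criteria that section 5.0 leaves open should be listed.

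The cost is a sentence or two in section 6.7 and a short list. No new data are needed, since eligibility deviations are already reported and adverse events are collected from consent. No rule on who may be treated changes. The observed rates may be slightly less favourable.
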